1.3 SCHEDULE OF ACTIVITIES (SOA)

The schedule of activities (SoA) for patients who complete the planned treatment is described in Section 1.3.1. Patients who withdraw from treatment prematurely must complete the ETD visit and follow the assessment in Section 1.3.2 for the remaining visits.

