1.3.2 Reduced schedule of events for patients after early treatment discontinuation

	ETD2																													
	ETD ^a								,						,		,								٠,				,	
VISIT		3	4		5		6		7 ^j		8 ^j		9		10 ^j		11 ^j		12		13/		14	_	15		16	17 ^j	18 ^j	19
WEEK		2	4	6	8	10	12	14	16	18	20	22	24	26	28	30	32	34	36	38	40	42	44	46	48	50	52	56	60	64 (EOS)
BODE score, includes 6-minute walk test and mMRC Dyspnea scale	X																													
Smoking status	Х	Х	Х		Х		Х		Х		Х		Х		Х		Х		Х		X		Х		Х		Χ	X	Х	Х
Prior & concomitant medications	Х		Х		Х		Х		Х		Х		Х		Х		Х		Х		X		Х		Х		Χ	X	Х	Х
Study treatment administration																														
Call IVRS/IWRS	X																													X
Review electronic diary	X																										Х			Х
Safety																														
Physical examination ^C	X	Г											Х														X			Х
Vital signs ^d	X		Х		Х		Х						Х						X				Χ				Х			Х
Electrocardiogram (12 lead) ^b	X						Χ						Χ						X								Х			Х
Hematology, biochemistry, urinalysis including cotinine ^{e, f}	x						х						х						x								x			х
Urine pregnancy test ^g	X		X		X		X		X		X		X		X		X		X		X		X		X		X			X
Adverse event reporting, including SAEs	х	X	X		х		Х		х		Х		Х		Х		x		x		X		X		Х		X	X	х	X
Pharmacokinetics																														
Serum PK samples for dupilumab concentration	X						Х						Х						х								X			
Anti-dupilumab antibody	X						Х						Х														X			
Biomarkers																														
FeNO post-bronchodilator	X						Х						Х						X								X			X
PARC	X																													
Eotaxin-3	X																													Х
Total IgE	X																													X
Fibrinogen	X																													X
Whole blood RNA (optional)	X																													
Serum/plasma for archival samples (optional)	X																													

	ETD ^a																													
VISIT		3	4		5		6		7 j		8 ^j		9		10 ^j		11 ^j		12		13 ^j		14		15 ^j		16	17 ^j	18 ^j	19
WEEK		2	4	6	8	10	12	14	16	18	20	22	24	26	28	30	32	34	36	38	40	42	44	46	48	50	52	56	60	64 (EOS)
Efficacy																														
COPD exacerbation reporting by the Investigator	X	X	X		х		Х		Х		Х		X		Х		x		х		Х		Х		Х		X	X	X	X
Spirometry (pre-BD) ^h	Х		Х		Х		Х						X						Х				Х				X			X
Spirometry (post-BD) ^h	Х		Χ		Х		X						X						X								X			Х
EXACT ⁱ	X																													
SGRQ ⁱ	Х						Х						X						Х								X			X
EQ-5D-5L ⁱ	Х																													
Health care utilization	X																										X			

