- e Hematology will include hemoglobin, hematocrit, platelet count, total white blood cell count, differential count, and total red blood cell count. Serum chemistry will include creatinine, blood urea nitrogen, glucose, lactate dehydrogenase, uric acid, total cholesterol, total protein, albumin, total bilirubin, alanine aminotransferase, aspartate aminotransferase, alkaline phosphatase, electrolytes (sodium, potassium, chloride), bicarbonate, and creatine phosphokinase. Urinalysis will include specific gravity, pH, glucose, ketones, blood, protein, nitrate, leukocyte esterase, urobilinogen and bilirubin. If any parameter on the dipstick is abnormal, a urine sample should be sent to the central laboratory for quantitative measurement. If positive for protein and/or red blood cells, microscopic analysis will be performed by the central laboratory.
- f Refer to central lab manual for collection details.
- g Only for women of childbearing potential. Urine pregnancy test at ETD and every 4 weeks through Visit 16 and at EOS. In case of positive urinary test, a serum pregnancy test should be performed as soon as possible to confirm the pregnancy. Pregnancy testing should be done monthly, female participants will be supplied with dipsticks for between on-site visits.
- h Spirometry will be done locally according to European Respiratory Society (ERS)/American Thoracic Society (ATS) 2005 guidance but measured by a central laboratory. Spirometry will be performed during a trough period of bronchodilators according to their action duration, for example, withholding the last dose of salbutamol/albuterol or levosalbutamol/levalbuterol for at least 6 hours, withholding the last dose of LABA for at least 12 hours (ultra-long acting LABA like vilanterol should be withheld for at least 24 hours) and withholding the last dose of LABA for at least 24 hours. This will be verified before performing the measurements. Note: When both pre- and post-bronchodilator spirometry is assessed, the post-bronchodilator spirometry should be performed consistent with the mechanism of action of reliever (ie, 30 minutes for albuterol or other SABA).
- i The EQ-5D-5L, EXACT, and SGRQ are to be completed in the patient's electronic diary.
- i Telephone visit.

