2.1.3.2.2 Exploratory/Tertiary efficacy endpoints

2.1.3.2.2.1 Exacerbations of chronic pulmonary disease tool (EXACT)

The EXACT tool quantifies and measures exacerbations of COPD and assesses the symptomatic manifestations of these COPD exacerbations (see Appendix D). The instrument is a daily diary composed of a total of 14 items representing the following domains:

- Breathlessness (5 items),
- Cough and sputum (2 items),
- Chest symptoms (3 items),
- Difficulty bringing up sputum (1 item),
- Tired or weak (1 item),
- Sleep disturbance (1 item), and
- Scared or worried (1 item).

The EXACT total score assesses COPD exacerbations. The higher the score, the more severe are the symptoms.

The EXACT questionnaire is assessed daily from screening to Visit 16 (Week 52). Baseline EXACT score as well as the post-baseline weekly scores will be calculated as the mean within-patient score over the prior 7 days, with data present for a minimum of 4 of the 7 days. If fewer than 4 days of data are available in the 7-day window, the EXACT score cannot be calculated and will be considered as missing. For the exacerbation analysis, the baseline would be reset during

the study. Additional information related to computing scores and frequency, severity, and duration of events can be found in the user manual (6).

The Evaluating Respiratory Symptoms (E-RS) in COPD (E-RS: COPD) scale is a part of the EXACT tool. It is a derivative instrument used to measure the effect of treatment on the severity of respiratory symptoms in stable COPD. The E-RS utilizes the 11 respiratory symptom items contained in the 14-item EXACT.

The daily COPD RS-Total score is computed by taking the sum of the 11 items comprising the instrument. It has a range of 0 to 40, with higher values indicating more severe respiratory symptoms.

The same summation procedure is used to derive the three daily domain scores:

- COPD RS-Breathlessness (sum of items 7, 8, 9, 10, and 11; score range 0–17)
- COPD RS-Cough and Sputum (sum of items 2, 3, 4; score range 0–11)
- COPD RS-Chest Symptoms (sum of items 1, 5, 6; score range 0–12)

Like for EXACT, the baseline RS score as well as the post-baseline weekly domain and total scores are calculated as the mean within-patient score over the prior 7 days, with data present for a minimum of 4 of the 7 days. If fewer than 4 days of data are available in the 7-day window, the RS scores cannot be calculated and will be considered as missing.

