2.4.4.3 Multiplicity issues

Multiplicity is considered for performing an interim analysis and for testing multiple endpoints. The overall Type-I error rate will be controlled at the two-sided 0.05 level.

An interim analysis will be performed using the Kim-DeMets (9) spending function when the information fraction is ≥ 0.92 based on follow-up time for the primary endpoint of annualized rate of moderate or severe COPD exacerbations over 52-week treatment period (see [Section 3](#)).

A hierarchical testing procedure will be used for testing primary, key secondary and other endpoints. If the primary endpoint does not demonstrate efficacy at this interim analysis then the study will remain blinded and the primary endpoint will be retested at the 52-week final analysis time point with an $\alpha=0.049$. If the primary endpoint demonstrates efficacy at this interim analysis based on the alpha allocated, then the rest of the multiplicity-controlled endpoints will be tested with $\alpha=0.05$. The comparisons will be tested based on the hierarchical order below.

1) Primary efficacy endpoints:

- Annualized rate of moderate or severe COPD exacerbations over the 52-week treatment period compared to placebo.

2) Secondary/exploratory efficacy endpoints:

- Change in pre-bronchodilator FEV₁ from baseline to Week 12 compared to placebo
- Change in pre-bronchodilator FEV₁ from baseline to Week 52 compared to placebo
- Change in pre-bronchodilator FEV₁ from baseline to Week 12 compared to placebo in the subgroup of patients with baseline FeNO ≥ 20 ppb
- Change in pre-bronchodilator FEV₁ from baseline to Week 52 compared to placebo in the subgroup of patients with baseline FeNO ≥ 20 ppb
- Change from baseline to Week 52 in SGRQ total score compared to placebo
- Proportion of patients with SGRQ improvement ≥ 4 points at Week 52 compared to placebo
- Change in E-RS COPD total score from baseline to Week 52 compared to placebo
- Annualized rate of moderate or severe COPD exacerbation compared to placebo over the 52-week treatment period in the subgroup of patients with baseline FeNO ≥ 20 ppb

The study is considered positive when the primary endpoint achieves statistical significance.

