Secondary endpoint – Continuous	Change from baseline in FEV ₁ at Week 12 Change from baseline in FEV ₁ at Week 52 Change from baseline in SGRQ at Week 52 Change from baseline in E-RS at Week 52 ^b	ITT (For FEV ₁ endpoints, also patients with baseline FeNO ≥ 20 ppb)	
The intercurrent events will be handled as follows:
 
 Discontinuing the study intervention prior to Week 12 or Week 52: all data collected after discontinuation will be used in the analysis (treatment policy strategy). 
In addition, the missing data imputation rules are as follows:
 
 Missing data will be imputed latently by MMRM based on missing at random assumption 	MMRM model using change from baseline in corresponding endpoint values up to corresponding weeks as response variables, and factors for treatment group, age, sex, height (age, sex and height are only included for spirometry endpoints analyses), region (pooled country), ICS dose at baseline, smoking status at screening, visit, treatment-by-visit interaction, baseline value of the endpoint, and baseline-by-visit interaction as covariates.

Endpoint Category	Estimands			
	Endpoint(s) ^a	Population	Intercurrent event(s) handling strategy and missing data handling	Population-level summary
Secondary endpoint – Proportion	Proportion of SGRQ improvement (≥ 4 points) at Week 52.	ITT	
The intercurrent events will be handled as follows:
 
 Discontinuation of study intervention prior to Week 52: Off-study intervention data will be included in the analysis (treatment policy strategy). 
In addition, the missing data imputation rules are as follows:
 
 Having missing data at Week 52: Participants will be considered as non-responders. 	Logistic regression model, with treatment group, region (pooled country), ICS dose at baseline, smoking status at screening, and baseline SGRQ total score as covariates
Secondary objective: To evaluate the effect of dupilumab on moderate and severe COPD exacerbations				

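### The documents conflict on whether the daily EXACT diary continues after early treatment discontinuation; if it does not, the Week 52 E-RS test cannot deliver its treatment-policy label, and no specified analysis would show the gap

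*SAP*

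**What the plan says.** **Status of the endpoint.** SAP 2.4.4.3 lists "Change in E-RS COPD total score from baseline to Week 52 compared to placebo" second to last in the testing order: eighth of nine counting the primary, just before exacerbations in the subgroup with baseline FeNO of at least 20 ppb. A footnote to Appendix L calls it exploratory.

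**Estimand.** Appendix L puts E-RS in one row with FEV1 and SGRQ. For treatment discontinuation the row says "all data collected after discontinuation will be used in the analysis (treatment policy strategy"; for missing values, "Missing data will be imputed latently by MMRM based on missing at random assumption".

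**Collection after stopping treatment.**
- Protocol 1.3: "Patients who withdraw from treatment prematurely must complete the ETD visit and follow the assessment in Section 1.3.2 for the remaining visits".
- Protocol 1.3.2 ("Reduced schedule of events for patients after early treatment discontinuation"): the EXACT row has one mark, at ETD. SGRQ and pre-bronchodilator spirometry remain scheduled to Week 64.
- Protocol 1.3.1 has a daily EXACT line to Week 52, but that schedule is for patients who complete treatment.
- SAP 2.1.3.2.2.1: "The EXACT questionnaire is assessed daily from screening to Visit 16 (Week 52"), with no exception for patients off treatment. A weekly score is a 7-day mean "with data present for a minimum of 4 of the 7 days".

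**Sensitivity analyses.** SAP 2.4.4.6 promises pattern-mixture and other sensitivity analyses but refers to 2.4.4.1, which models exacerbation events only. Appendix K covers exacerbations and Week 12 FEV1.

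**The concern.** A treatment-policy estimate needs outcomes after treatment stops. FEV1 and SGRQ have off-treatment visits in the reduced schedule. E-RS, in the same Appendix L row, has none after ETD if that schedule governs. There would then be essentially no post-discontinuation data for the strategy to use. The MMRM would fill Week 52 for discontinuers from patients still under observation, nearly all on treatment. The result would be close to the effect had everyone stayed on treatment, reported as treatment policy. At stake are the size and meaning of an alpha-controlled symptom result, and, through the testing order, access to the FeNO-subgroup exacerbation test that follows it.

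**Working it through.** **Plan figure.** The plan gives no effect size, SD, power or discontinuation rate for E-RS, so there is nothing to reproduce for this test. Its one sample-size figure, for the primary endpoint, does reproduce: (1.960 + 1.282)² × [(1/(0.95 × 1.5) + 1) + (1/(0.95 × 1.125) + 1)] / ln(0.75)² = 461.8, so 462 per arm. It has no bearing on E-RS.

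**Step 1: what is observed at Week 52.** SAP 2.5.2 (Table 5) sets the Week 52 E-RS window at Days 359 to 365, and at least 4 of those 7 days are needed. Under Protocol 1.3.2, a patient whose ETD visit is before Day 359 has 0 scheduled entries in it. The score is missing by design.

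**Step 2: what the MMRM then estimates.** Let D be the on-treatment effect at Week 52, d the share stopping treatment before Week 52, and r the share of benefit retained at Week 52 by those who stopped. Stopping placebo is assumed to change nothing. Then:
- treatment-policy effect = D × [1 − d(1 − r)]
- MMRM without off-treatment data ≈ D
- relative overstatement = 1 / [1 − d(1 − r)] − 1

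Both d and r are assumptions. Protocol 7.1.1 calls permanent discontinuation rare but gives no rate.

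| d | r = 1 | r = 0.5 | r = 0 |
|---|---|---|---|
| 5% | 0 | 2.6% | 5.3% |
| 10% | 0 | 5.3% | 11.1% |
| 15% | 0 | 8.1% | 17.6% |
| 20% | 0 | 11.1% | 25.0% |

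Example: d = 10%, r = 0 gives 1/0.90 − 1 = 11.1%.

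**Step 3: simulation check.** The settings were 462 per arm, 13 time points, maximum likelihood under missing at random, D = −0.20 SD, r = 0 and 400 runs per case. Treatment-policy versus model estimates were −0.187 and −0.198 (d = 5%), −0.180 and −0.200 (10%), and −0.157 and −0.197 (20%). This agrees with the formula within simulation error. With no drug effect, both were about 0.

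**Step 4: the schedule's share.** Patients who stop treatment and also leave the study have no Week 52 score under any schedule. Take d = 10%, r = 0, and assume half of those stopping also leave. With diaries collected from the half who stay, the model gives about D × 90/95, against a treatment-policy effect of 0.90D. The overstatement is (90/95)/0.90 − 1 = 5.3%. So of the 11.1%, about 11.1 − 5.3 = 5.8 points come from the schedule. The table figures are totals, and upper bounds for that share.

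**Step 5: how a reference-based analysis would behave.** Jump-to-reference gives about D(1 − d). At r = 0.5 its ratio to the true treatment-policy effect is 0.95/0.975 = 0.974 for d = 5% and 0.80/0.90 = 0.889 for d = 20%. That is 2.6% to 11.1% too small, equal and opposite to the MMRM error at that r. It is closer than the MMRM when less than half the benefit is retained, and further off when more is.

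**The case against.** **Off-treatment diaries may well have been intended.** Protocol 8.1.2.1 ends daily recording only in the Post IMP Treatment Period, which Protocol 4.1 defines as the 12 weeks after the 52-week period. A patient off drug at Week 30 is still within the planned treatment period. SAP 2.4.4.5.3 analyses EXACT-defined exacerbations over 52 weeks in the same way as the primary endpoint, which counts off-treatment events. A visit grid is also a poor place to show a daily item. All this stands and is why the point is conditional: a reader might infer that no diary was collected after ETD, but the documents do not establish that. Nor do they establish the opposite. Protocol 1.3 makes the reduced schedule mandatory, and the diary's continued use does not settle the matter, because SGRQ is entered on the same device ("The EQ-5D-5L, EXACT, and SGRQ are to be completed in the" patient's electronic diary).

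**The SAP does commit to sensitivity analyses.** SAP 2.4.4.6 promises to examine missing-data patterns and run pattern-mixture analyses. That stands too, so it would be wrong to say missing data are ignored. But the method it points to cannot be applied to a weekly symptom score. Describing missingness shows how much is missing, not its effect on the estimate. If the Week 12 FEV1 methods were carried over by analogy, the multiple imputation with treatment in the model also assumes missing at random and would reproduce the gap. A tipping-point analysis could probe it, but none is written for E-RS.

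**Appendix L discloses its missing-at-random rule.** True. If benefit fully persists, the overstatement is 0. The label is misleading only if benefit fades.

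**Conclusion.** The conflict between Protocol 1.3.2 and SAP 2.1.3.2.2.1 is real and needs resolving. If the reduced schedule governs, the planned E-RS analysis estimates roughly an on-treatment effect under a treatment-policy label, and no specified analysis would reveal it. Total overstatement is 2.6% to 11.1% with half the benefit retained and 5.3% to 25.0% with none, at an assumed 5% to 20% stopping treatment. Only part of this belongs to the schedule.

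Two stronger readings are not supported. One is a false-positive risk: in the model used here the on-treatment and treatment-policy effects are zero together, so no type I error inflation is shown. The other is damage to the main results: the primary, FEV1 and SGRQ tests come earlier in the order and have scheduled off-treatment data. It would, however, be too narrow to say that only E-RS is touched, because its result gates the FeNO-subgroup exacerbation test. Severity is minor: the endpoint is labelled exploratory and is eighth of nine.

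**What to change.** Before unblinding:

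1. Reconcile Protocol 1.3.2, Protocol 8.1.2.1 and SAP 2.1.3.2.2.1, and state in the SAP whether daily EXACT was collected after ETD.
2. If it was not, either give E-RS its own Appendix L row with a hypothetical strategy for treatment discontinuation, or keep treatment policy and state that it rests on imputation.
3. In either case, add to Appendix K one reference-based multiple imputation of E-RS at Week 52, with the variant named. Jump-to-reference is one reasonable choice; say that it is conservative if benefit is partly retained. It is supplementary if the main estimand is relabelled, and a sensitivity analysis to missing at random otherwise.
4. Correct the 2.4.4.6 cross-reference so that continuous endpoints lead to a method for continuous endpoints.

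The cost is SAP wording and one extra analysis. The SAP already plans a control-based imputation for the primary endpoint, so the approach is not new to the trial. If the estimand is relabelled, the E-RS claim no longer covers the period after stopping treatment.
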